Chronic GVHD is a major source of morbidity, mortality, and impaired quality of life after HCT. Despite prophylactic immune suppressive agents delivered prior to and following HCT, the majority of patients will develop chronic GVHD. The currently accepted primary therapy of chronic GVHD, namely 1mg/kg or greater of prednisone or equivalent, is ineffective, and available immune suppressive agents have limited activity in those who fail primary therapy. These all speak to the need for more effective primary therapy for chronic GVHD. Based on compelling clinical and basic insights into chronic GVHD biology, anti-CD20 based therapy has great potential to improve the success of chronic GVHD therapy. Thus, we propose a phase I-II study of combined ofatumumab and standard glucocorticoids to study the safety and efficacy of this approach.

II. STUDY OBJECTIVES

Primary Objectives:

1. Phase I: Determine the safety of ofatumumab in combination with steroids in the primary therapy of chronic GVHD
2. Phase II: Determine overall response rate (CR+PR) at 6 months to ofatumumab and glucocorticoid primary therapy of chronic GVHD.

Secondary Objectives:

1. Determine 6 month complete response rate to ofatumumab and steroids in the primary therapy of chronic GVHD.
2. Examine cumulative incidence of non-relapse mortality and primary disease relapse, and estimate overall survival from time of therapy.
3. Report utilization of second-line immune suppressive therapies.
4. Examine incidence of complete discontinuation of immune suppressive therapy .
5. Determine failure-free survival (composite outcome of death, relapse and requirement for secondary immune suppressive agents) and treatment success (composite outcome defined as complete resolution of all reversible chronic GVHD manifestations, discontinuation of all systemic immune suppressive agents, and freedom from death or primary malignancy relapse).
6. Evaluate serial measures of patient-reported outcomes following therapy, including functional ability, symptom burden, and quality of life.
7. Perform allied biologic studies for total B cells, B cell subsets, immune globulin levels, BAFF levels, and examine association between these biologic endpoints and clinical response to primary therapy.

III. STUDY DESIGN AND ENROLLMENT CRITERIA

Summary of Trial design

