- vi. Plan for patients not able to be evaluated for outcome on phase I component:
 1. If an enrolled patient dies or comes off study following occurrence of DLT as defined above, this data will inform the

determination of DLT, and there will be no need to replace such patients.

2. Rather, if an enrolled patient does not experience DLT during follow up, but decides to withdraw from the study for other non-DLT related reasons prior to the minimum follow up of 46 days, such a patient would be replaced by a newly accrued patient.

2. Efficacy

a. Overall response rate

- i. Overall response rate (ORR) at 6 months following initiation of therapy represents the composite outcome of complete and partial response (CR + PR).
- ii. Complete response is defined as resolution of all reversible manifestations in each organ or site of chronic GVHD involvement
- iii. Partial response is defined as improvement in at least one organ or site without progression in any other organ or site

b. Complete response rate

- i. Complete response (CR) at 6 months following initiation of therapy requires complete resolution of all chronic GVHD manifestations in all affected organs.

c. Cumulative incidence of non-relapse mortality and primary malignancy relapse

- i. The cumulative incidence of non-relapse mortality (defined as death in the absence of primary malignancy relapse after transplant) and relapse (defined by usual definitions in clinical practice including, but not limited to morphologic, immunophenotypic, or molecular methods) will be estimated from time of study therapy initiation. These are treated as competing-risk events.

d. Overall survival

- i. Overall survival will be determined from date of study therapy initiation, with death from any cause as the event of interest, and censoring at last follow up date for those with incomplete observations.

e. Utilization of second-line systemic immune suppressive therapies

- i. The use of second-line systemic immune suppressive agents will be captured at each study visit.
- ii. This specifically refers to systemic therapies only, not topical or local therapies, such as topical eye drops, mouth rinses, topical steroid skin cream, or topical vaginal steroid agents.

- iii. Adjustment in prednisone dose according to disease manifestations is not considered second-line therapy

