a. Phase I (those patients in dose levels that are not the MTD to be carried forward into the phase II component)

i. patients will complete 46 days of follow up from last dose of ofatumumab to monitor for DLT

ii. for those not in the MTD cohort, limited data will be collected at 6 and 12 months (clinical response, pharmacodynamics)

b. Phase II (including patients who are carried forward from the phase I component) – patients will complete 24 total months of follow up on study

e. Clarification on duration of follow up and assessments for phase I patients

a. As the MTD will not be known in real-time, patients on any of the phase I dose levels may potentially be those carried forward from the MTD cohort as the recommended phase II dose

b. Accordingly, patients in all dose levels of the phase I trial will need to have all of the above outlined on-study assessments performed until the MTD is defined.

c. Once the MTD is defined, only those patients in the MTD cohort will continue to have all of the ongoing assessments performed

d. Conversely, those in the non-MTD cohorts will complete an abbreviated assessment measure set to include only the chronic GVHD activity assessments/response determination and the biologic studies (B cell

subsets, BAFF levels) at 6 and 12 month time points. These limited assessments for the non-MTD dose level patients will be included to examine the relationship between dose and clinical response, and dose/pharmacodynamic activity.

VI. STATISTICAL ANALYSIS:

Study design and sample size estimation:

In the phase I component, dose escalation procedure is modeled after the data reported for ofatumumab in treatment of rheumatoid arthritis. Here, doses of 300, 700, and 1000mg were delivered on days 0 and 14. As this dose/schedule was well tolerated, led to significant and sustained (up to 48 weeks) depletion of peripheral blood CD19+ B cells, and there was an association between escalating dose and clinical response ([appendix A](#)), this dose/schedule will be adapted to a phase I design in the primary treatment of chronic GVHD.

The study design of the phase I component represents a traditional (3+3) dose escalation design with the following cohorts of ofatumumab in combination with 1mg/kg/day prednisone therapy:

(cohort -1): 100mg days 0 and 14

cohort 1: 300mg days 0 and 14

cohort 2: 700mg days 0 and 14

cohort 3: 1000mg days 0 and 14

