Following definition of the maximal tolerated dose (MTD) in the phase I component, this MTD will be taken forward in a phase II trial to characterize the efficacy of this approach. The primary endpoint of interest in the phase II component is overall response rate (ORR) to therapy at 6 months. Overall response is defined as the composite of complete response and partial response. In the assessment of response for this primary endpoint, response will be determined according to clinician assessment. The Simon's two-stage optimum design is used to minimize the expected sample size. With a historical baseline ORR proportion of 60% (*justification for this baseline proportion in background section*), anticipated effect leading to ORR of 80% in this investigational treatment (prednisone + ofatumumab), power of 90%, and alpha of 0.1, a total of 38 subjects are needed for this analysis of efficacy. As 6 total patients from the phase I component will have been treated at the recommended phase II dose, these will be included for efficacy analysis. Early termination will occur if 6 or fewer out of 11 ($\leq 6/11$) subjects in first stage have a overall response (CR or PR). If the trial goes on the second stage and a total number of responders (CR or PR) is less than or equal to 26 ($\leq 26/38$), the null hypothesis fails to be rejected. To provide total of 38 subjects for this efficacy analysis, 32 additional patients will be enrolled in the phase II component. Thus, the net total number of patients to be enrolled on the combined phase I-II study will be a maximum of 50.

Statistical Analysis plan:

The 'All Treated population' will be used for the analysis of the efficacy and safety endpoints. Specifically, this will consist of all patients who receive at least one dose of study treatment. For Complete Response (CR) rate and Overall Response rate: A

patient with unknown or missing response will be treated as a non-responder (i.e. the patient will be included in the denominator when calculating the percentage).

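### The efficacy population has no dose limit, so read literally the reported response rates pool off-dose phase I patients whom the 26/38 test leaves out

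*Combined protocol and SAP*

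**What the plan says.** All references are to the combined protocol and SAP.

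- **Section VI, Phase II component.** The ORR test is a Simon two-stage design. The six phase I patients treated at the recommended phase II dose count towards it, and "To provide total of 38 subjects for this efficacy analysis, 32 additional patients will be enrolled in the phase II component". The trial stops if 6 or fewer of the first 11 respond. The null hypothesis is not rejected if 26 or fewer of 38 respond. The paragraph adds that "the net total number of patients to be enrolled on the combined phase I-II study will be a maximum of 50".
- **Section VI, Statistical Analysis plan.** The All Treated population "will be used for the analysis of the efficacy and safety endpoints", and "this will consist of all patients who receive at least one dose of study treatment". A missing or unknown response counts as non-response and stays in the denominator. ORR at 6 months is reported with a 95% confidence interval, and the CR rate is reported in the same way.
- **Section II.** The ORR objective belongs to one phase: "Phase II: Determine overall response rate (CR+PR) at 6 months".
- **Section V.4.e.** Once the maximum tolerated dose (MTD) is defined, "only those patients in the MTD cohort will continue to have all of the ongoing assessments performed". Patients at other doses keep response assessment and biologic studies at 6 and 12 months, and these "will be included to examine the relationship between dose and clinical response".
- **Section III, Inclusion Criteria.** Phase I takes only moderate or severe chronic GVHD. Phase II takes any severity that needs systemic therapy.

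**The concern.** Two efficacy denominators stand in adjacent paragraphs. The test uses 38 patients at one dose. The formal population definition takes in everyone dosed, at any level, and nothing elsewhere narrows it for efficacy.

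A programmer who follows the definition would report an ORR, a confidence interval and a CR rate from a different set of patients from those behind the go/no-go decision. The estimate would mix dose levels. It would also give more weight to patients selected for moderate or severe disease. The same set would serve the other efficacy endpoints, although off-dose patients have only abbreviated assessments after the MTD is defined.

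**Working it through.** **1. The plan's own design reproduces.** Inputs from Section VI, Phase II component: null ORR 0.60, target ORR 0.80, alpha 0.1, power 90%, stage 1 rule 6/11, final rule 26/38. Stage 2 has 38 − 11 = 27 patients. With b the binomial probability,

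P(reject | p) = Σ (x = 7 to 11) b(x; 11, p) × P(Bin(27, p) ≥ 27 − x).

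- p = 0.60: 0.0970, within the 0.1 limit; probability of stopping at stage 1 is 0.467.
- p = 0.80: 0.9042, meeting the 90% target.

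A search of two-stage designs under these limits returns 6/11 and 26/38 as the optimum. The design belongs to 38 patients, and 6 + 32 = 38.

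**2. How many off-dose patients the definition admits.** Section VI (Phase I trial procedures and analysis) puts the maximum phase I accrual at roughly 12 to 18. Six of these are at the recommended dose.

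| Phase I total | Off-dose patients | All Treated at full accrual | Off-dose share |
|---|---|---|---|
| 12 | 12 − 6 = 6 | 38 + 6 = 44 | 6/44 = 14% |
| 18 | 18 − 6 = 12 | 38 + 12 = 50 | 12/50 = 24% |

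The second row matches the stated maximum of 50. Other phase I totals are possible, because a cohort can close early on toxicity and some early withdrawals are replaced. The table therefore shows the range the plan itself gives, not every path.

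**3. Shift in the expected ORR.** With m off-dose patients and an off-dose ORR that differs from the on-dose ORR by d points, the pooled ORR shifts by m/(38 + m) × d. The documents give no dose-response figure for ofatumumab in chronic GVHD, so d is an assumption: on-dose ORR 80%, d from −20 to +20.

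- N = 44: 6/44 × 20 = 2.7 points, so a pooled ORR of 77.3% to 82.7%.
- N = 50: 12/50 × 20 = 4.8 points, so a pooled ORR of 75.2% to 84.8%.

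**4. An example at the decision boundary.** The smallest positive result is 27/38 = 71.1% (exact 95% CI 54.1% to 84.6%). If 7 of 12 off-dose patients respond, the literal definition reports (27 + 7)/(38 + 12) = 34/50 = 68.0% (exact 95% CI 53.3% to 80.5%). The plan does not name an interval method; Clopper-Pearson is assumed here.

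**5. Case mix.** The intended set already holds 6 phase I patients of 38 (16%). The literal set at the maximum holds 18 of 50 (36%), all selected for moderate or severe disease.

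**The case against.** The strongest reply is that the documents already identify the efficacy set. The Phase II component paragraph names the six recommended-dose patients as included and counts to 38, which implies that other phase I patients are excluded. Section V.4.e gives off-dose response data a separate use, the study of dose and response. The Early Stopping Rule for Toxicity also speaks of 38 phase II patients. On this view the All Treated sentence only sets an at-least-one-dose rule and the handling of missing responses. As evidence of intent this is right, and it keeps the severity low. It does not change the definition, which covers efficacy and carries no dose limit.

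Three stronger readings are tempting, and the documents do not support them.

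- **That the primary test loses its error control.** Carrying the cut-off of 26 over to 50 patients would give a type I error of 0.496 when all have an ORR of 60%. The plan prints the cut-off as 26 of 38, so the rule keeps its own denominator.
- **That pooling must lower the ORR.** Section VI asserts a dose-response association in rheumatoid arthritis, but the figures quoted in the background are not monotone. In Study 403 Part B, ACR20 response was 40%, 49% and 44% at 300, 700 and 1000 mg. In follicular lymphoma, response was 63%, 33%, 20% and 50% at 300, 500, 700 and 1000 mg. The range in the working is therefore two-sided.
- **That patient-reported and functional outcomes are wholly missing off-dose.** Section V.4.e requires full assessments at every dose level until the MTD is defined. These data would be partial.

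Extreme results are also arithmetically possible: 27/38 could be reported as anything from 27/50 (54.0%) to 39/50 (78.0%). The ends need none or all of 12 off-dose patients to respond, so they should not set the severity.

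**Conclusion.** The point holds as a low-severity error in the definition of the efficacy population. Followed literally, it puts 14% to 24% off-dose patients into the reported ORR, its interval, the CR rate and other efficacy estimates. The expected shift in ORR is at most 2.7 points at 44 patients and 4.8 points at 50, in an unknown direction. This rests on an assumed on-dose ORR of 80%, off-dose ORR within 20 points either way, full phase II accrual and 12 or 18 phase I patients. The go/no-go decision does not change, and the intended set is evidently the 38. The correction is still worth making, because a primary analysis set should be stated and not left to inference.

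**What to change.** Reword the population paragraph in Section VI, Statistical Analysis plan, along these lines:

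*ORR, CR rate and all other phase II efficacy endpoints are analysed in all patients who receive at least one dose of ofatumumab at the recommended phase II dose (planned n = 38: 6 from phase I and 32 from phase II). A missing or unknown response counts as non-response. The All Treated population, at all doses, is used for safety. Response at other phase I doses is tabulated by dose and is not pooled with the efficacy population.*

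The 6/11 and 26/38 rules stay as printed. The cost is a few lines of SAP wording, with no extra patients, visits or data.

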 - iv. Adjustment in the dose of existing immune suppressive agents that require dose modification to maintain therapeutic serum drug levels (e.g. tacrolimus, cyclosporine, sirolimus) is not considered a second-line therapy or change in therapy
 - v. New initiation of extra-corporeal photopheresis (ECP) for progressive chronic GVHD manifestations following study intervention of prednisone and ofatumumab is considered second-line therapy.
- f. Discontinuation of all systemic immune suppressive therapies
- i. The incidence of complete discontinuation of all systemic immune suppressive therapies will be determined.
- g. Failure-free survival
- i. This time-to-event outcome will be estimated with the composite event of death from any cause, relapse and addition of secondary immune suppressive agents for progressive chronic GVHD.
- h. Treatment success
- i. This endpoint will be estimated with a composite outcome of complete resolution of all reversible chronic GVHD manifestations, discontinuation of all systemic immune suppressive agents, and freedom from death or primary malignancy relapse after transplant.
- i. Patient-reported outcomes and functional measures
- i. Patients will provide assessment of their functional ability (grip strength, 2 minute walk test), symptom burden (Lee symptom scale), and quality of life using validated instruments recommended by the NIH Consensus Development Project on Chronic GVHD (Lee Chronic GVHD Symptom Scale,⁴¹ HAP functional scale,⁴² QOL instruments SF-36⁴³ and FACT-BMT⁴⁴)
 - ii. These data will be collected at baseline, 3, 6, and 12 months on study
- j. Biologic studies

Peripheral blood samples will be obtained from study patients at baseline, and then 3, 6, and 12 months. From these peripheral blood samples, the following major analyses will be performed: (1) quantification of plasma B cell stimulatory factor (BAFF), (2) quantification of immune globulin levels, and (3) enumeration of total B cells, as well as characterization of B cell subsets by surface phenotype through flow cytometric analysis.

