From whole blood samples, plasma will be separated, and utilized for determination of soluble BAFF levels by enzyme-linked immunosorbent assay (ELISA). From peripheral blood mononuclear cells (PBMC), B cells will be isolated. Antibodies targeting surface antigens CD19, CD20, CD38, CD27, and IgD will be utilized for staining, and the respective cell subsets will be characterized by flow cytometry according to phenotype: Naïve B cells (IgD⁺CD38^{Low}CD27⁻), transitional B cells (IgD⁺CD38^{High}CD27⁻), IgD⁺ memory B cells (IgD⁺CD38^{Low}CD27⁺), pre-germinal center B cells (IgD⁺CD38^{High}CD27⁺), post-germinal center memory B cells (IgD^{Low}CD38^{Low}CD27⁺), and plasmablast/plasma cell (IgD^{Low}CD38^{High}CD27⁺).

3. Summary of pre-treatment and on-study testing to be performed

- Pre-treatment assessments / screening

- i. Evaluation of eligibility: Inclusion, exclusion criteria
- ii. Laboratory studies (CBC with differential, chemistry, liver function tests, review of prior hepatitis B and C, as well as HIV testing – may utilize prior HIV/hepatitis testing done for purpose of transplant eligibility)
- iii. Pregnancy - Women of childbearing potential must have current negative pregnancy test, and both men and women must agree to adequate contraception methods.
- iv. EKG
- v. assessment of Karnofsky Performance Status (KPS)

- On-study assessments (windows described in study calendar)

- i. history and physical examination, standard laboratory tests (CBC, chemistry, LFT)
- completed screening, day 0, day 14, months 1, 3, 6, 9, 12, 18, 24
- ii. Chronic GVHD activity
- completed screening, day 14, months 1, 3, 6, 9, 12, 18, 24
- includes scoring of chronic GVHD severity per NIH 0-3 severity, clinician-reported severity measures, patient reported severity
- includes recording of immune suppressive medications at each visit
- iii. Patient-reported outcomes
- completed screening, day 14, months 1, 3, 6, 9, 12, 18, 24

- includes quality of life, Lee symptom scale, and HAP (human activity profile)

iv. Functional measures

- completed screening, day 14, months 1, 3, 6, 9, 12, 18, 24

- includes grip strength and 2 minute walk test

v. Biologic samples

- baseline, then months 3, 6, 12

- includes the above-described B cell subset studies and BAFF levels

4. Criteria for patient termination from study

a. Patient decision to withdraw from study

b. Death

c. Relapse of primary hematologic malignancy

d. End of study

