Overall response (ORR) rate will be determined at 6 months and will be reported with associated 95% confidence interval. Complete response rate will be similarly reported. Association between clinical variables (chronic GVHD severity, organ involvement, patient socio-demographic data, disease and transplantation variables) and response will be examined. Patient reported outcomes will be reported, and association between scores on individual measures (chronic GVHD symptom scale, human activity profile, QOL instruments including SF-36 and FACT-BMT) and clinical response to therapy will be explored. Cumulative incidence of relapse and non-relapse mortality will be estimated, accounting for competing risk events. Overall survival from date of therapy initiation will be estimated by Kaplan-Meier method, and survival curves among relevant subgroups will be compared utilizing the log-rank test. In the analysis of survival time between responders and non-responders, landmark analysis will be utilized to avoid biased survival estimation. Other time-to-event secondary endpoints (e.g. failure-free survival) will similarly be estimated using the Kaplan-Meier method. Biologic endpoints (total B cell numbers, B cell subsets, immune globulin levels, BAFF levels) will be summarized. Comparisons between relevant groups will be made at specific time points utilizing parametric (e.g. t-test) or non-parametric (e.g. Wilcoxon rank-sum) as appropriate per the nature of the data. Additionally, change in these values over time will be examined according to response vs. non-response to primary therapy with mixed-model approach.

Early Stopping Rule for Toxicity

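### Kaplan-Meier is the only method stated for the remaining time-to-event secondary endpoints; applied to stopping all immune suppression, it would overstate incidence because death and relapse compete

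*Combined protocol and SAP*

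**What the plan says.** The Statistical Analysis plan in Section VI assigns methods to the time-related endpoints in three steps.

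- Relapse and non-relapse mortality: "Cumulative incidence of relapse and non-relapse mortality will be estimated, accounting for competing risk events". Section V.2.c agrees: "These are treated as competing-risk events".
- Overall survival: Kaplan-Meier.
- Everything else of this type: "Other time-to-event secondary endpoints (e.g. failure-free survival) will similarly be estimated using the Kaplan-Meier method".

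Failure-free survival is the only example named. Section V.2.g defines it so that death and relapse are themselves events: "This time-to-event outcome will be estimated with the composite event of death from any cause, relapse and addition of secondary immune suppressive agents".

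Three further efficacy endpoints in Section V.2 receive no method by name.

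- Discontinuation of immune suppression: the objective in Section II is "Examine incidence of complete discontinuation of immune suppressive therapy", and Section V.2.f adds only "The incidence of complete discontinuation of all systemic immune suppressive therapies will be determined".
- Second-line therapy: the objective is "Report utilization of second-line immune suppressive therapies", and Section V.2.e has use recorded at every visit.
- Treatment success (Section V.2.h): a composite that requires, among other things, that the patient has neither died nor relapsed.

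Section V.4 lists "Relapse of primary hematologic malignancy" among the reasons a patient leaves the study. Phase II follow-up is 24 months.

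**The concern.** A patient who dies on treatment can never come off immune suppression or start a second-line agent. A patient who relapses leaves the study, so later changes in immune suppression are not observed under the protocol. Kaplan-Meier handles both as ordinary censoring: it assumes these patients would go on to have the event at the same rate as those still followed. The complement of the curve then estimates incidence in a hypothetical setting without death or relapse, and it exceeds the proportion of treated patients who actually have the event.

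For discontinuation, the error makes the regimen look better than it is. For second-line use, it makes the regimen look worse. The plan already recognises the problem for relapse and non-relapse mortality, so leaving it open here is an internal gap.

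**Working it through.** **Step 1. Which endpoints does the catch-all sentence reach?** Section V.2 lists ten efficacy endpoints, a to j.

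- Overall and complete response (a, b) are proportions.
- Relapse and non-relapse mortality (c) have a competing-risk method.
- Overall survival (d) and failure-free survival (g) have Kaplan-Meier.
- Patient-reported and functional measures (i) and biologic studies (j) are not time-to-event.

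This leaves second-line therapy (e), discontinuation (f) and treatment success (h). The catch-all is plural and gives failure-free survival as an example only, so if it covers anything more, it covers one or more of these three. Discontinuation is the clearest candidate: it is called an incidence and has no other estimator. The rule that counts a missing outcome as a failure in Section VI is confined to complete and overall response, so it does not supply a method either.

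**Step 2. Is Kaplan-Meier sound where it is named?** Yes. When every competing event counts as an event, Kaplan-Meier equals one minus the sum of the cumulative incidences. In 5,000 simulated trials of 38 patients, the two agreed to rounding error (mean 45.1% event-free by both routes). Failure-free survival is not affected.

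**Step 3. Size of the overstatement if it is applied to discontinuation.** The plan states no figure to reproduce, so the rates below are assumptions. Let Fe be the true 24-month cumulative incidence of the event and Fc that of death or relapse occurring first. With constant cause-specific hazards:

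- total cumulative hazard H = −ln(1 − Fe − Fc)
- share due to the event = Fe / (Fe + Fc)
- one minus Kaplan-Meier = 1 − exp(−H × share)

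Worked case, Fe = 30% and Fc = 20%: H = −ln(0.50) = 0.693; share = 0.30/0.50 = 0.60; result = 1 − exp(−0.416) = 34.0%.

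| Assumed Fc | One minus Kaplan-Meier (true Fe = 30%) | Overstatement, points |
|---|---|---|
| 10% | 31.8% | 1.8 |
| 20% | 34.0% | 4.0 |
| 30% | 36.8% | 6.8 |
| 40% | 40.3% | 10.3 |

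Over a wider grid (Fe 20% to 50%, Fc 10% to 40%), the overstatement runs from 1.2 to 22.2 points. The top of that range needs Fe = 50% and Fc = 40%, which leaves only 10% of patients free of both.

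**Step 4. Check at the planned sample size.** In the same simulation (38 patients, Fe = 30%, Fc = 25%), mean one minus Kaplan-Meier was 35.3%, against a mean cumulative incidence estimate of 30.0%. The bias does not depend on large samples.

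**The case against.** The strongest reply is that the plan never says it will use Kaplan-Meier for these endpoints. A reader might infer that the catch-all prescribes it for all three. The documents do not go that far: only failure-free survival is labelled time-to-event. Second-line use is to be reported as utilization, which a simple proportion would satisfy, and a proportion could also pass as the incidence of discontinuation. This part of the reply stands, and it is why the point is conditional for second-line therapy. It does not remove the point for discontinuation: if the sentence does not apply there, the plan has no estimator, time point or competing-event rule for that endpoint at all.

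A reader might also infer that treatment success is biased in the same way. It is not, if reported as a fixed-time proportion, because a patient who dies or relapses fails the definition and stays in the denominator. The bias would arise only in a time-to-success analysis that censored those patients, and the plan describes none.

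Nor do the definitions of discontinuation and second-line use exclude relapsed patients. Relapse matters because it ends participation, so later events go unobserved. Treating it as a competing event is a reasonable choice of estimand, not something the definitions dictate.

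Finally, the size can be small. With 38 patients, the standard error of a 30% estimate is about √(0.3 × 0.7 / 38) = 7.4 points, so an overstatement of 2 to 7 points lies within one standard error. That is fair as to importance, but a systematic error in a known direction is still worth removing when removal costs almost nothing.

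**Conclusion.** The point holds in conditional form. Kaplan-Meier is the only estimator the plan states for time-to-event secondary endpoints other than relapse and non-relapse mortality. It is right for overall and failure-free survival. Applied to discontinuation of all systemic immune suppression, or to second-line therapy over time, it would overstate incidence: by about 2 to 10 points at an assumed true 24-month incidence of 30% with 10% to 40% competing events. These figures rest on constant hazards and on rates the documents do not give. The direction does not depend on those rates: whenever competing events precede some of the events of interest, one minus Kaplan-Meier is the larger figure.

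Only secondary descriptive estimates are affected. The primary response endpoint, the two-stage decision rule and the toxicity boundary are untouched. This is a cheap improvement, not a flaw in the design.

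**What to change.** In the Statistical Analysis plan of Section VI:

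- Restrict the Kaplan-Meier sentence to overall survival and failure-free survival.
- Add that discontinuation of all systemic immune suppression and time to second-line systemic therapy will be estimated by cumulative incidence (Aalen-Johansen), with death and relapse as competing events.
- Add that treatment success will be reported as a proportion at a stated time, with death and relapse counted as non-success, or by cumulative incidence.

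The cost is a sentence or two in the plan and a little more analysis work, using a method already planned for relapse and non-relapse mortality. The reported discontinuation rate will be somewhat lower than one minus Kaplan-Meier would have shown.
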